Nephritis: grading according to increased creatinine or acute kidney injury	Grade 2 Grade 3 or 4	Withhold Permanently discontinue	Administer corticosteroids (prednisone 1 to 2 mg/kg or equivalent) followed by taper	Monitor changes of renal function
Neurological Toxicities	Grade 2 Grade 3 or 4	Withhold Permanently discontinue	Based on severity of AE administer corticosteroids	Ensure adequate evaluation to confirm etiology and/or exclude other causes
Myocarditis	Grade 1 Grade 2, 3 or 4	Withhold Permanently discontinue	Based on severity of AE administer corticosteroids	Ensure adequate evaluation to confirm etiology and/or exclude other causes
Exfoliative Dermatologic Conditions	Suspected SJS, TEN, or DRESS Confirmed SJS, TEN, or DRESS	Withhold Permanently discontinue	Based on severity of AE administer corticosteroids	Ensure adequate evaluation to confirm etiology or exclude other causes
All Other irAEs	Persistent Grade 2 Grade 3 Recurrent	Withhold or discontinue based on the event e	Based on severity of AE administer corticosteroids	Ensure adequate evaluation to confirm etiology or exclude other causes
	Recurrent Grade 3 or Grade 4			

AE(s)=adverse event(s); ALT= alanine aminotransferase; AST=aspartate aminotransferase; CTCAE=Common Terminology Criteria for Adverse Events; DRESS=Drug Rash with Eosinophilia and Systemic Symptom; GI=gastrointestinal; IO=immuno-oncology; ir=immune related; IV=intravenous; SJS=Stevens-Johnson Syndrome; T1DM=type 1 diabetes mellitus; TEN=Toxic Epidermal Necrolysis; ULN=upper limit of normal.

Note: Non-irAE will be managed as appropriate, following clinical practice recommendations.

^a AST/ALT: >3.0 to 5.0 x ULN if baseline normal; >3.0 to 5.0 x baseline, if baseline abnormal; bilirubin:>1.5 to 3.0 x ULN if baseline normal; >1.5 to 3.0 x baseline if baseline abnormal

	Toxicity			
	Grade	Action With		
	(CTCAE	Pembrolizuma	Corticosteroid and/or	
irAEs	v5.0)	b	Other Therapies	Monitoring and Follow-up

- AST/ALT: >5.0 to 20.0 x ULN, if baseline normal; >5.0 to 20.0 x baseline, if baseline abnormal; bilirubin:>3.0 to 10.0 x ULN if baseline normal; >3.0 to 10.0 x baseline if baseline abnormal
- c AST/ALT: >20.0 x ULN, if baseline normal; >20.0 x baseline, if baseline abnormal; bilirubin: >10.0 x ULN if baseline normal; >10.0 x baseline if baseline abnormal
- d The decision to withhold or permanently discontinue pembrolizumab is at the discretion of the investigator or treating physician. If control achieved or ≤ Grade 2, pembrolizumab may be resumed.
- ^e Events that require discontinuation include, but are not limited to: encephalitis and other clinically important irAEs (eg, vasculitis and sclerosing cholangitis).

Patient should receive appropriate supportive care measures as deemed necessary by the treating physician. Suggested supportive care measures for the management of AEs with potential immunologic etiology are outlined along with the dose modification guidelines in the table above. Where appropriate, these guidelines include the use of oral or IV treatment with corticosteroids, as well as additional anti-inflammatory agents if symptoms do not improve with administration of corticosteroids. Note that several courses of steroid tapering may be necessary as symptoms may worsen when the steroid dose is decreased. For each disorder, attempts should be made to rule out other causes such as metastatic disease or bacterial or viral infection, which might require additional supportive care. The treatment guidelines are intended to be applied when the Investigator determines the events to be related to pembrolizumab.

Note: If after the evaluation of the event, it is determined not to be related to pembrolizumab, the Investigator does not need to follow the treatment guidance. Refer to the table above for guidelines regarding dose modification and supportive care. It may be necessary to perform conditional procedures such as bronchoscopy, endoscopy, or skin photography as part of evaluation of the event.

Note: For grade 1 or grade 2 amylase and/or lipase, in the absence of symptomatic pancreatitis, patients will continue with treatment. Treatment with pembrolizumab will be withheld for grade 3 amylase and/or lipase changes, or if symptoms of pancreatitis with grade 2 amylase and/or lipase. Pembrolizumab may be resumed if asymptomatic and laboratory changes are \leq grade 2.

Pembrolizumab may cause severe or life threatening infusion-reactions including severe hypersensitivity or anaphylaxis. Signs and symptoms usually develop during or shortly after drug infusion and generally resolve completely within 24 hours of completion of infusion. Dose modification and toxicity management guidelines on pembrolizumab associated infusion reaction are provided in the Table below:

NCI CTCAE Grade	Treatment	Premedication at Subsequent Dosing		
Grade 1	Increase monitoring of vital signs as medically	None		
Mild reaction; infusion	indicated until the participant is deemed medically			
interruption not indicated;	stable in the opinion of the investigator.			
intervention not indicated				
Grade 2	Stop Infusion.	Participant may be premedicated 1.5h (±		
Requires therapy or	Additional appropriate medical therapy may include	30 minutes) prior to infusion of		
infusion interruption but	but is not limited to:	pembrolizumab with:		
responds promptly to	IV fluids	Diphenhydramine 50 mg po (or		
symptomatic treatment	Antihistamines	equivalent dose of antihistamine).		
(e.g., antihistamines,	NSAIDs	Acetaminophen 500-1000 mg po (or		
NSAIDs, narcotics, IV	Acetaminophen	equivalent dose of analgesic).		
fluids); prophylactic	Narcotics			
medications indicated for	Increase monitoring of vital signs as medically			
≤24 hrs	indicated until the participant is deemed medically			
	stable in the opinion of the investigator.			
	If symptoms resolve within 1 hour of stopping drug			
	infusion, the infusion may be restarted at 50% of the			
	original infusion rate (e.g. from 100 mL/hr to 50			
	mL/hr). Otherwise dosing will be held until			
	symptoms resolve and the participant should be			
	premedicated for the next scheduled dose.			
	Participants who develop Grade 2 toxicity despite			
	adequate premedication should be permanently			
	discontinued from further study drug treatment			
Grades 3 or 4	Stop Infusion.	No subsequent dosing		
Grade 3:	Additional appropriate medical therapy may include			
Prolonged (i.e., not rapidly	but is not limited to:			
responsive to symptomatic	Epinephrine**			
medication and/or brief	IV fluids			
interruption of infusion);	Antihistamines			
recurrence of symptoms	NSAIDs			
following initial	Acetaminophen			
improvement;	Narcotics			
hospitalization indicated	Oxygen			
for other clinical sequelae	Pressors			
(e.g., renal impairment,	Corticosteroids			
pulmonary infiltrates)	Increase monitoring of vital signs as medically			
Grade 4:	indicated until the participant is deemed medically			
Life-threatening; pressor	stable in the opinion of the investigator.			
or ventilatory support	Hospitalization may be indicated.			
indicated	**In cases of anaphylaxis, epinephrine should be used			
	immediately.			
	Participant is permanently discontinued from			
	further pembrolizumab treatment.			
Appropriate resuscitation equipment should be available at the bedside and a physician readily available during the period of drug				

Appropriate resuscitation equipment should be available at the bedside and a physician readily available during the period of drug administration.

For further information, please refer to the Common Terminology Criteria for Adverse Events v. 4.0 (CTCAE) at http://ctep.cancer.gov

8.1 Dosing Delay (reasons other than treatment related AEs):

Pembrolizumab may be interrupted for situations other than treatment-related AEs such as medical / surgical events or logistical reasons not related to study therapy. Participants should be placed back on study therapy within 3 weeks of the scheduled interruption, unless otherwise discussed with the Sponsor. The reason for interruption should be documented in the patient's study record. When the subject resumes treatment with pembrolizumab they should skip the missed cycle and resume at the next cycle (i.e. skip C7 and resume at C8D1).

If a vaccine only visit needs to be delayed/missed for reasons other than treatment related AEs, reach out to Sponsor Investigator for further guidance.

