received vaccines at every 2-week intervals and pembrolizumab at every 3-week intervals. Emerging data from animal studies has suggested that "density" of vaccination (every week rather than every 2 weeks) is preferable for initiating an immune response, but periods of time between booster immunization may be important for establishing immune memory. In order to accommodate these observations into a workable schedule, the current trial will aim for two vaccinations per 3-week cycle with pembrolizumab, and using two such cycles consecutively prior to alternating vaccine. In addition, because most patients with metastatic prostate cancer have bone metastases, a site that is difficult to characterize objectively, a subset of patients treated at the University of Wisconsin Carbone Cancer Center will undergo NaF PET/CT with site-directed biopsies to determine if this modality can identify early metabolic signals associated with immune infiltration as an early treatment biomarker. An exploratory aim will be to determine whether treatment elicits changes in the gut microbiome, and whether clinical response is associated with changes in the composition of the gut microbiome. Based on published studies and our own prior experience, the median time to disease progression in this stage of disease is approximately 3 months. Hence the use of 6-month progression-free survival provides a clinically relevant endpoint, and a basis for comparing the two treatment arms. Patients without progression at 6months will continue with pembrolizumab alone until PSA rise, at which point vaccine courses will be restarted. This approach will permit evaluation of second courses of treatment in responding individual. Overall, identification of PSA responses (defined as PSA decline > 50%), objective radiographic responses, as well as delays in the time to disease progression, will serve as evidence of clinical activity to compare the treatment arms and be used for planning future confirmatory clinical trials.

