3. OBJECTIVES

H. Primary Objective

To determine the 6-month progression-free survival rate in patients with metastatic, castration-resistant prostate cancer (mCRPC) treated with pembrolizumab in combination with one versus two DNA vaccines as T-cell activating agents

I. Secondary Objectives:

- 1. To determine the overall objective response rate (using Prostate Cancer Working Group 3 (PCWG3) criteria)
- 2. To determine the PSA response rate (decline > 50%)
- 3. To determine the median radiographic progression-free survival rate
- 4. To determine median duration of PSA and/or objective response in responding individuals
- 5. To determine the overall survival
- 6. To determine whether the development of antigen-specific Th1 immunity elicited with treatment to either antigen (PAP or AR) is associated with PSA response

- 7. To evaluate the safety and tolerability of pTVG-HP DNA vaccine with or without pTVG-AR DNA vaccine and pembrolizumab
- J. Laboratory and Exploratory Objectives:
- 1. To evaluate PAP-specific and AR-specific antibody responses following treatment with pembrolizumab and DNA vaccine(s)
 - 2. To determine whether treatment with either sequence elicits immunologic antigen spread to other prostate associated antigens
 - 3. To determine whether pre-existing antigen-specific immunity is predictive of immunological or objective clinical response
 - 4. To determine, in a subset of patients, whether early changes in bone observed by NaF PET/CT are associated with immunological or objective clinical response, or pathological changes associated with immune-cell infiltration
 - 5. To determine second PSA response rates in patients treated in follow-on courses
 - 6. To determine whether treatment elicits changes in the gut microbiota composition
 - 7. To determine whether changes in gut microbiota are associated with clinical response (PSA decline > 50%)

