While PSA values will be collected, and PSA kinetics (PSA responses and maximal changes in PSA by waterfall plots) monitored as an endpoint, PSA rise will not be used to determine objective disease progression. Similar to the radiographic studies above, PSA progression or response will be defined using pre-treatment (study entry) as baseline values.

- a. **PSA Complete Response:** Decrease in PSA to <0.2 ng/mL and confirmed with PSA measurement a minimum of four weeks later (confirmed PSA CR). There must be no evidence of radiographic progression.
- b. **PSA Partial Response**: Greater than or equal to 50% reduction in baseline PSA. There must be no evidence of radiographic progression.
- c. **Best Response**: This is calculated from the sequence of objective statuses. The date of response will be defined as the first date at which PSA declined from baseline or normalized.
- d. **Confirmed PSA PR**: Two or more objective statuses of PSA PR or better a minimum of four weeks apart documented before progression. Best response for objective disease must be stable/no response or better.
- e. **Unconfirmed PSA PR**: One objective status of PSA PR documented before progression, but not qualifying for confirmed PSA PR. Best response for objective disease must be Stable/no response or better.
- f. **No PSA Response**: Objective PSA status does not qualify as a PSA PR or unconfirmed PSA PR.
- g. **Inadequate Assessment, response unknown**: When best response for objective disease is inadequate or unknown or when PSA has been inadequately assessed, then PSA response will be coded likewise.
- h. **PSA Progression**: Although not considered progression per the primary objective of this study, time to PSA progression will be used for secondary analyses. PSA progression will be defined as a **100%** increase in PSA over the nadir PSA, and ≥ 2 ng/mL above the nadir, confirmed by a second value 3 or more weeks later (i.e. confirmed rising trend). If no on-study reduction has occurred, nadir would be the baseline value.

5. Evaluation of Patient's Best Overall Response

The best overall response is the best response recorded from baseline until disease progression/recurrence, taking as reference for progressive disease the smallest measurements recorded after baseline. The table below provides overall responses for all possible combinations of tumor responses in target and nontarget lesions, with or without new lesions.

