To be assigned a status of complete or partial response, changes in tumor measurements must be confirmed by repeat assessments performed **no less than four weeks** after the criteria for response are first met.

To be assigned a status of stable disease, measurements must have met the stable disease criteria at least once after study entry at a minimum interval of 12 weeks.

6. Overall Response for all Possible Combinations of Tumor Response

Target	Nontarget	New	Overall		
Lesions	Lesions	Lesions	Response		
CR	CR	No	CR		
CR	Incomplete	No	PR		
	response/SD				
PR	Non-PD	No	PR		
SD	Non-PD	No	SD		
PD	Any	Yes or No	PD		
Any	PD	Yes or No	PD		
Any	Any	Yes	PD		

CR = complete response; PR = partial response; SD = stable disease; PD = progressive disease

A. First Documentation of Response

The time between initiation of therapy and first documentation of PR or CR.

B. Confirmation of Response

To be assigned a status of complete or partial response, changes in tumor measurements must be confirmed by repeat assessments performed **no less than four weeks** after the criteria for response are first met.

C. Duration of Response

Duration of overall response – the period measured from the time that measurement criteria are met for complete or partial response (whichever status is recorded first) until the first date that recurrent or progressive disease is objectively documented, taking as reference the smallest measurements recorded since treatment started.

1. Duration of Overall Complete Response

The period measured from the time measurement criteria are met for complete response until the first date that recurrent disease is objectively documented.

2. Duration of Stable Disease

A measurement from baseline until the criteria for disease progression is met, taking as reference the smallest measurements recorded since baseline. To be assigned a status of stable disease, measurements must have met the stable disease criteria at least once after study entry at a minimum interval of 12 weeks.

D. Overall Survival

Overall survival (OS) will be defined as the time interval from randomization to death from any cause or to the last follow-up in censored patients.

E. Progression Free-Survival

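### PSA response is dated at the first PSA decline of any size, not when the 50% (or <0.2 ng/mL) criterion is met; a PSA response duration run from that date can only be equal or too long

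*Combined protocol and SAP*

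**What the plan says.** **Response thresholds.** Section 7.B.4 defines PSA partial response (item b) as "Greater than or equal to 50% reduction in baseline PSA" and PSA complete response (item a) as "Decrease in PSA to <0.2 ng/mL and confirmed with PSA measurement a minimum of four weeks later". Items d and e recognise both confirmed and unconfirmed PSA partial responses.

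**Response date.** Item c, headed Best Response, says: "The date of response will be defined as the first date at which PSA declined from baseline or normalized". No minimum size is attached to the decline, and the term for normalization is not defined.

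**Duration.** Secondary objective 4 (Sections 3 and 11) is "To determine median duration of PSA and/or objective response in responding individuals". The Duration of Response paragraph in Section 7 (7.C) defines duration of overall response as "the period measured from the time that measurement criteria are met for complete or partial response", ending at objectively documented recurrence or progression.

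**What is absent.** No section states where PSA response duration starts, where it ends or how it is censored. The analysis of secondary endpoints in Section 11 has no paragraph on duration of response.

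**The concern.** A patient is a PSA responder only once PSA has fallen by at least half, yet item c dates the response at the first fall. Suppose PSA is down 3% at cycle 2 and first reaches a 50% decline at cycle 5. Item c dates the response at cycle 2, although on that day the patient would have been classed under item f as having no PSA response. With 21-day cycles that is 3 × 3 = 9 weeks early.

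This runs against the plan's own practice elsewhere. Both 7.C and the paragraph on first documentation of response tie the start to reaching partial or complete response. At stake is the median duration of PSA response. If item c supplies the start, part of the reported duration is time before the patient met the definition of response. The extra time is longest in patients whose PSA falls slowly or late.

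**Working it through.** The plan states no figure for PSA response duration, so there is nothing to reproduce. The check has a logical part, which is certain, and an illustration, which rests on assumptions.

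**1. Direction.** Let A be the dates on which PSA is below baseline, and B the dates on which PSA is at least 50% below baseline, or has fallen below 0.2 ng/mL. Every date in B is also in A, so the earliest date in A is never later than the earliest date in B. With a common end date, duration from item c equals duration from the criterion plus a lag of zero or more.

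**2. Size, with exact PSA values.**

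Inputs:
- PSA is drawn on day 1 of each 21-day cycle (study calendar; Section 9), so visits fall at weeks 3, 6, 9 and so on.
- Assumption, not in the documents: PSA falls steadily from the start of treatment, PSA(t) = PSA(0) × 2^(−t/h), with halving time h in weeks.

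The first decline is seen at week 3. The first value at or below 50% is seen at week 3 × ceil(h/3). The lag is the difference. Its relative effect on an assumed true duration D is lag/D.

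| Halving time h (weeks) | Item c date (week) | First decline of at least 50% (week) | Lag (weeks) | Lag/D, D = 12 | D = 24 | D = 36 |
|---|---|---|---|---|---|---|
| 3 | 3 | 3 | 0 | 0% | 0% | 0% |
| 6 | 3 | 6 | 3 | 25% | 12.5% | 8% |
| 9 | 3 | 9 | 6 | 50% | 25% | 17% |
| 12 | 3 | 12 | 9 | 75% | 37.5% | 25% |
| 18 | 3 | 18 | 15 | 125% | 62.5% | 42% |

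The values of D are also assumptions.

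**3. Adding assay noise (assumed).** In a simulation with 5% or 10% noise, the mean lag is 1.5 weeks for a 3-week halving time and 4.5 weeks for 6 weeks. These exceed the exact-value lags because the 50% point falls on a visit, and noise often pushes the first qualifying value to the next one. If the true fall starts only at week 6 or week 9, with a 6-week halving time, the mean lag is 8.0 or 10.3 weeks: a chance dip in a flat PSA already sets the item c date. No simulated lag was negative, as step 1 requires.

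**4. Which start date governs PSA duration?** Item c gives a response date specific to PSA but sits under Best Response. The 7.C paragraph gives a rule for duration but is written for overall response and ends at objective progression, which Section 7.B.4 says a PSA rise does not determine. A PSA-specific end point is available in item h, "increase in PSA over the nadir PSA, and ≥ 2 ng/mL above the nadir, confirmed by a second value 3 or more weeks later", but the plan does not say that it ends the duration. The two candidate starts disagree whenever the first decline is smaller than 50%.

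**The case against.** The strongest reply is that nothing in the plan says PSA duration runs from item c. The only text headed as duration is 7.C, which starts when criteria are met. Section 7.B.4 uses the same partial and complete response labels for PSA, so an analyst could carry 7.C over and no bias would arise. This stands as a limit: a reader might infer that the reported duration will be overstated, but the documents support only the conditional statement. It does not clear item c, which would then contradict the rule actually used.

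A second reply is that item c refers to the sequence of objective statuses, so its wording may be shorthand for the partial and complete responses of items a and b. If any fall counted, mentioning normalization would add nothing. That may be the intent, but the sentence as written carries no threshold.

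Two further inferences are not supported. A reader might take objective 4 to mean that PSA and objective durations are pooled; its and/or wording prescribes no pooled analysis, and Section 11 describes none. A reader might also set the lags against the median time to progression of about 3 months in Section 2. That figure describes patients at this stage of disease generally, not PSA responders, and is no benchmark for response duration.

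Finally, Section 11 promises a detailed SAP before the final analysis, and the PSA values are collected each cycle anyway. Both points make the problem easy to repair; neither removes it.

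**Conclusion.** The point holds in conditional form. Item c states a response date that does not match the plan's own definition of PSA response and conflicts with 7.C. That is an incorrect stated rule, not merely a missing detail. If PSA response duration is measured from item c, it will be equal to or longer than the true duration, never shorter. The direction follows from the definitions alone.

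The size cannot be derived from the documents. It is illustratively 0 to 9 weeks for assumed halving times of 3 to 12 weeks, with 3-weekly PSA and exact values. For a patient whose PSA halves by the first on-treatment draw it is zero.

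The effect is confined to the PSA part of one secondary objective, for which no between-arm test is specified. The primary endpoint, the PSA response rate and the power calculation are unaffected. The correction is worth making before analysis but does not threaten the trial's main conclusion.

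**What to change.** Replace the dating sentence in item c with: *The date of PSA response is the first date on which PSA is at least 50% below baseline (PR) or <0.2 ng/mL (CR).* State that duration of PSA response is measured from that date, consistent with 7.C.

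For confirmed responses, use the date of the first qualifying value, not the confirming one. Do not make confirmation a condition for having a response date: the plan also recognises unconfirmed PSA partial response, and those patients would otherwise have no date and drop out of the duration analysis.

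The detailed SAP should also name the event that ends PSA response duration, give the censoring rule, and say whether unconfirmed responses enter the analysis.

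Cost: one sentence in Section 7 and a short paragraph in the SAP. No new data are needed. The downside is that the reported duration may be somewhat shorter.

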A treatment-limiting toxicity will be defined as any Grade 3 or greater toxicity (using the NCI Common Terminology Criteria version 4), or a specific Grade 2 event as described below that affects agent dosing, with an attribution of at least possibly related to the study or treatment procedures, and occurring between the pre-study visit and within one month of the final study vaccine treatment or within 90 days of the last treatment with pembrolizumab (whichever is later). If a patient develops Grade 3 toxicity with an attribution of at least possibly related to pembrolizumab and unlikely related (or unrelated) to pTVG-HP or pTVG-AR vaccine, the pembrolizumab treatment will be held until the toxicity resolves to Grade 1 or less, with the vaccine schedule continuing as per protocol. If the adverse event is considered immune-related, both pembrolizumab and pTVG-AR (and/or pTVG-HP) will be held until the toxicity resolves to Grade 1 or less. If a patient develops a second Grade 3 event (or any Grade 4 event) believed to be at least possibly due to pembrolizumab, but unlikely related (or unrelated) to pTVG-HP or pTVG-AR vaccine, no further pembrolizumab treatments will be given. The patient will continue with DNA vaccine administration only as per protocol, if the adverse event is not immune-related. If immune-realted, both the pembrolizumab and vaccine(s) will be discontinued. However, if a patient develops a Grade 3 toxicity with an attribution of at least possibly related to pTVG-HP or

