pTVG-AR vaccine, both vaccine(s) and pembrolizumab treatment will be held until the toxicity resolves to Grade 1 or less. If a patient develops a second Grade 3 event (or any Grade 4 event) believed at least possibly related to pTVG-HP or pTVG-AR vaccine, no further treatments will be given. Patients will not have any dose modifications (or change in dose or schedule) of pembrolizumab in this study except as noted in section 8.1. If the toxicity does not resolve, or the criteria for resuming treatment (to Grade 1 or less as in the table below) are not met, the patient will discontinue pembrolizumab (and continuing vaccinations, if the adverse event was not believed to be immune-mediated), or discontinue both study medications (vaccine and pembrolizumab) if the adverse event was considered immune-mediated and the vaccinations were already being held. The patient will remain on study, however, with collection of radiographic and laboratory data as per protocol. The rationale for these modifications is that patients could continue to benefit in terms of anti-tumor response and this could in fact be related to the development of other autoimmune toxicities, and patients who have non-immune related toxicity from pembrolizumab could still potentially benefit from continued DNA vaccination. While rare overall, autoimmune events observed following pembrolizumab treatment of patients with melanoma typically resolved and did not necessarily lead to discontinuation of treatment.

If a subject has to hold treatment for a visit, confirm with the sponsor that the subject should skip the current visit and resume treatment at the next timepoint (i.e. if a subject has to hold drug at C7D1 due to an AE, the patient would skip C7D1, be reevaluated at C7D8 and if necessary to continuing holding, come back and resume treatment at C8D1, if allowable per protocol).

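### Section 8 holds and restarts pembrolizumab after a first Grade 3 event in its general rule, but stops it permanently in the infusion-reaction table and five irAE rows, with no statement of which governs

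*Combined protocol and SAP*

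**What the plan says.** The opening paragraphs of Section 8 set a general rule for Grade 3 events. If the event is attributed to pembrolizumab and not to a vaccine, "the pembrolizumab treatment will be held until the toxicity resolves to Grade 1 or less, with the vaccine schedule continuing as per protocol". If it is immune-related, "both pembrolizumab and pTVG-AR (and/or pTVG-HP) will be held until the toxicity resolves to Grade 1 or less". If a vaccine may have contributed, "both vaccine(s) and pembrolizumab treatment will be held until the toxicity resolves to Grade 1 or less".

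Under this rule pembrolizumab stops for good in two situations. One is a repeat or worse event: "If a patient develops a second Grade 3 event (or any Grade 4 event) believed to be at least possibly due to pembrolizumab". The other is failure to recover, or where "the criteria for resuming treatment (to Grade 1 or less as in the table below) are not met". The same text adds: "Patients will not have any dose modifications (or change in dose or schedule) of pembrolizumab in this study except as noted in section 8.1". Section 8.1 covers delays for reasons other than treatment-related adverse events.

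Two tables follow in Section 8. In the infusion-reaction table, the row for Grades 3 or 4 says "Participant is permanently discontinued from" further pembrolizumab, and its last column says "No subsequent dosing". The irAE table gives permanent discontinuation at Grade 3, without requiring recurrence, for pneumonitis, AST/ALT or bilirubin elevation, nephritis and neurological toxicity. For myocarditis it does so from Grade 2.

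**The concern.** For these events a site cannot follow both instructions, and each is in current text. The hold-and-restart branch also carries its own rationale: patients may still benefit, and autoimmune events with pembrolizumab usually resolved. A site that restarted would therefore be applying a reasoned rule.

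The infusion reaction is the clearest case. Section 8 says these reactions can be severe or life-threatening, yet usually clear within a day of the infusion. The restart condition of Grade 1 or less would then normally be met well before the next 21-day dose, and restarting re-exposes the patient to the agent that caused the reaction. For myocarditis, pneumonitis and the liver, kidney and neurological events, the danger is re-challenge after an organ toxicity for which the table ends treatment.

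The stake is patient safety and uniform handling across sites in an open-label, multi-institution trial.

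**Working it through.** The check is mainly a comparison of text.

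**1. The instructions side by side, first Grade 3 event related to pembrolizumab**

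| Event | General rule, Section 8 | Table, Section 8 |
|---|---|---|
| Infusion reaction | hold, restart at Grade 1 or less | permanent stop |
| Pneumonitis | hold, restart | permanent stop |
| AST/ALT or bilirubin | hold, restart | permanent stop |
| Nephritis | hold, restart | permanent stop |
| Neurological | hold, restart | permanent stop |
| Myocarditis | hold, restart | permanent stop (from Grade 2) |
| Hypothyroidism | hold at Grade 3, stop at Grade 4 | continue at Grades 2 to 4 |

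The irAE table has 12 rows. Five conflict in the unsafe direction. The others are not counted:
- colitis stops at recurrent Grade 3 or at Grade 4;
- T1DM/hyperglycemia is withheld;
- hypophysitis and hyperthyroidism are left to discretion;
- hypothyroidism differs the other way;
- exfoliative skin conditions depend on diagnosis, not grade;
- the residual row depends on the event.

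**2. Is there a precedence statement?** The general rule cites a table only for the restart criterion. The one exception named for dose or schedule changes is Section 8.1. The lead-ins to both tables introduce them as guidelines. The discontinuation criteria in Section 9 refer back to Section 8 for unacceptable adverse events. They also list recurrent Grade 2 pneumonitis separately, but none of the first-Grade-3 stops above. No sentence ranks the two instructions.

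**3. What can be counted for the infusion reaction.** After a Grade 3 reaction at cycle 1, the table allows 0 further infusions. Under the general rule, once restarted:
- 1, if the next dose causes a second Grade 3 event;
- 17 at the 12-month average treatment length in the Trial Summary: floor((365 − 1)/21) + 1 = 18 infusions, less the first;
- at most 32 − 1 = 31.

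These counts do not carry over to the irAE rows. The irAE table's general instructions require a steroid taper of at least 4 weeks before restart. That is 28 days against a 21-day cycle, so restart at cycle 2 is not available.

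**4. How often might a qualifying event occur?** The documents give no rate for infusion reactions or for single irAE rows. The only figure, in Section 6, is pooled: 139 of 2,799 melanoma or lung cancer patients had a Grade 3 immune-related event of special interest.
- Rate: 139/2,799 = 0.0497. Assuming it holds here, 60 × 0.0497 = 2.98 of 60 patients.
- The share *s* falling in the five rows is unknown. Expected events are 60 × 0.0497 × *s*, and the chance of at least one is 1 − (1 − 0.0497 × *s*)^60.

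| Assumed *s* | Expected patients | Chance of at least one |
|---|---|---|
| 10% | 0.3 | 26% |
| 50% | 1.5 | 78% |
| 100% | 3.0 | 95% |

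This is the chance that the conflict arises, not the chance that anyone is wrongly re-dosed.

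**The case against.** The other side has a good case on intent.
- The tables are more specific than the general rule.
- The lead-in to the irAE table directs that pembrolizumab be withheld or permanently stopped according to severity. The text after it says the guidance is meant for events the investigator attributes to pembrolizumab, and waives it only for unrelated events.
- The opening sentence of Section 8 anticipates particular Grade 2 events, described later, that affect dosing.
- Section 9 makes recurrent Grade 2 pneumonitis a mandatory stop. That trigger comes from the irAE table and cannot follow from the general rule, so Section 9 treats at least one table stop as binding.
- Sites must confirm with the sponsor when treatment is held, which gives one point of control.

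All of this stands, and most sites would probably follow the tables. It does not remove the conflict. Section 9 carries over one table stop and omits the first-Grade-3 stops. The sponsor check concerns skipping a visit and resuming as the protocol allows, which leads back to the same two instructions.

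A reader might also infer that the sentence limiting changes to Section 8.1 excludes the tables. The documents do not support that. The general rule itself orders holds and permanent stops outside Section 8.1, so the sentence cannot forbid the tables' stops. It simply fails to mention them.

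**Conclusion.** The conflict is real. It affects the infusion-reaction row and 5 of 12 irAE rows at a first Grade 3 event. The tables are very likely meant to govern, but the protocol never says so, and the general rule taken literally permits unsafe re-dosing. This should be corrected. It bears on safety and consistency between sites, not on the primary analysis.

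Two stronger readings should be resisted. A reader might infer that the plan intends re-dosing after these events; the context in Sections 8 and 9 points the other way. A reader might also take the 26% to 95% range, or the 17 or 31 infusions, as a measure of harm. The percentages rest on a rate from other tumor types and an assumed share, and describe only whether a qualifying event occurs. The infusion counts apply only to the infusion reaction, for which no frequency is given, and only once dosing has restarted. No frequency of wrong re-dosing can be derived.

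**What to change.** Add to the general rule in Section 8:

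> Where the irAE table or the infusion-reaction table requires permanent discontinuation of pembrolizumab, that requirement overrides the hold-and-restart rule in this paragraph. In particular, pembrolizumab is permanently discontinued after any Grade 3 or 4 infusion reaction, after a first Grade 3 pneumonitis or hepatic, renal or neurological irAE, and after myocarditis of Grade 2 or higher. If the event is immune-related, vaccination is also discontinued. In all other cases the stricter instruction applies.

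In the sentence that names Section 8.1 as the only exception, add the two tables.

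Giving the tables blanket precedence would not be safe. It would relax the general stop at Grade 4, since hypothyroidism continues at that grade, and footnote d lets T1DM/hyperglycemia, hypophysitis and hyperthyroidism resume at Grade 2 or less. It could also leave the vaccine merely on hold after an immune-related permanent stop. The sponsor should therefore state separately whether those endocrine rows are intended exceptions to the Grade 3 hold and the Grade 4 stop.

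The cost is a few sentences, with IRB approval as for any amendment. Design, sample size and data collection do not change.
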